4.2. Treatment Arms and Duration

The total duration of subject involvement is up to 10 weeks (Screening to Follow-up) as described below:

- Screening will be for at least 28 days prior to randomization. A window of ±2 days will be allowed for visits during the Screening period.
- Subjects who meet eligibility criteria will be randomized and begin dosing on Day 1. Subjects will discontinue their current ESA therapy and will be randomized to receive one of four three-times weekly doses, or placebo on a dialysis day as listed in Table 1. Examples of switching are provided in the Study Reference Manual (SRM).
 - This should be timed such that randomization (Day 1) occurs on the date that would have been the next scheduled dose of ESA (or as close as practicable).

- o For subjects with a three-times weekly dialysis schedule, Day 1 must not occur on the first dialysis session of the week (e.g., if Monday-Wednesday-Friday schedule, the study visit cannot be on Monday).
- o For subjects with a four- to five-times weekly dialysis schedule, Day 1 can be on any hemodialysis session of the week.
- The Treatment period will be for a total of 29 days. A window of ± 2 days is allowed for visits during the Treatment period.
 - At Day 29, all subjects will receive their last dose of study treatment and should not re-start ESA therapy until after the follow-up visit (Day 43).
 However, if the Investigator has a compelling clinical reason why a subject should restart ESA between Day 29 and Day 43, then ESA may be restarted prior to Day 43.
- A Follow-up visit will be scheduled to occur 14 ± 3 days after completing treatment.

Subjects will be randomized 1:1:1:1:1 to one of 5 treatment arms:

Table 1 Study Treatment Arm Descriptions

Treatment Arm	Description
А	10 mg GSK1278863 three-times weekly
В	15 mg GSK1278863 three-times weekly
С	25 mg GSK1278863 three-times weekly
D	30 mg GSK1278863 three-times weekly
Е	Placebo three-times weekly

Stopping algorithms are provided in Section 5.6.2 if Hgb values meet protocol prespecified ranges.

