7. STUDY ASSESSMENTS AND PROCEDURES

Protocol waivers or exemptions are not allowed with the exception of immediate safety concerns. Therefore, adherence to the study design requirements, including those specified in the Time and Events Table (Section 7.1), are essential and required for study conduct.

Time and Events Tables are provided in Section 7.1 for the overall study and for the specific Pharmacokinetic/Pharmacodynamic assessments (Table 2).

Study visit days are based on the schedule for hemodialysis as follows:

- Three times weekly: Hgb levels may have the greatest variability around study visits at the beginning of the week; therefore, the Day 1, 15 and 29 study visit must not occur on the first dialysis session of the week (e.g., if Monday-Wednesday-Friday dialysis schedule, then the study visit cannot be on Monday).
- **Four to five times weekly:** Designated study visit can be on any hemodialysis session of the week.

To allow scheduling flexibility, study visits should occur within a window of ± 2 days, except for subjects on a three times weekly dialysis schedule for whom study visits must not be scheduled on the first dialysis session of the week. Post-randomization visits should be referenced back to the Randomization visit (Day 1). In exceptional circumstances, minor changes to visit structure may be permitted after consultation with the GSK Medical Monitor.

The following points must be noted:

- If assessments are scheduled for the same nominal time, **THEN** the assessments should occur in the following order:
 - 1. 12-lead ECG
 - 2. Vital signs

3. Blood draws

NOTE: The timing of the assessments should allow the blood draw to occur at the exact nominal time.

- The change in timing or addition of time points for any planned study assessments must be documented in a Note to File which is approved by the relevant GSK study team member and then archived in the study sponsor and site study files, but this will not constitute a protocol amendment.
- The IRB/IEC will be informed of any safety issues that require alteration of the safety monitoring scheme or amendment of the Informed Consent Form.
- No more than 500 mL of blood will be collected over the duration of the study, including any extra assessments that may be required.

7.1. **Time and Events Table**

Protocol Activity 1,2	Screening			Treatment Period				Follow-up
110.00017.0.0015	Week -4	Week -2	Day 1	Day 15	Day 29	Un-scheduled	Early Withdrawal	Day 43 ± 3 6

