	
were not major protocol violators with regards to inclusion/exclusion criteria, investigational product compliance and concomitant medication instructions.
 
 Protocol deviations that would exclude subjects from the PP population are defined in Section 4.1 (Protocol Deviations) and Appendix 1 (Protocol Deviation Management and Definition for Per-Protocol Population). The Per-Protocol population will be used for sensitivity analyses. The Per-Protocol population will not be analyzed if this population comprises more than 80% of the Intent-To-Treat population. 	
Completer	
 Comprise all Intent-To-Treat subjects who fully completed the Day 29 study assessments without prematurely discontinuing study drug. The Completer Population will be used for sensitivity analyses. 	
 Efficacy
Pharmacokinetic Population	
 Comprises all subjects from whom a pharmacokinetic sample has been obtained and analyzed. 	
 PK

NOTES :

- Please refer to [Appendix 14](#): List of Data Displays which details the population to be used for each displays being generated.

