6.2.6. Exposure and Treatment Compliance

The complete dosing experience will be listed for all subjects. The total duration of exposure (number of days on study drug), average three times a week dose and cumulative dose will be summarized by treatment group and Dapro total.

The average three times a week dose (the cumulative actual dose divided by the expected number of doses during the treatment period) is calculated for each subject first and the summary statistics for each treatment group and for Dapro Total are calculated based on the subject average TIW dose.

$$\text{Cumulative actual dose} = \sum_{\text{bottle}=1}^3 \left(\frac{\text{No. of tablets taken from each bottle} *}{\text{tablet strength (mg/tablet)}} \right)$$

Note: The tablet strengths are 5 mg or 25 mg for subjects randomized to dapro arms, and 0 mg for subjects randomized to placebo arm (unless the subject received daprodustat by mistake during the study).

For subjects who completed the 29-day treatment period, the expected number of doses during the treatment period is 13. For subjects who permanently discontinued the study treatment and/or withdrew from the study, the expected number of doses during the treatment period will be calculated in the same way as the calculation of the expected cumulative number of tablets for each bottle described below for compliance calculation.

For each subject “Days on study drug” will be calculated as Last Dose Date – First Dose Date +1.

A summary and a listing of study medication compliance will be produced by treatment group.

For each bottle, the compliance will be calculated for the whole study treatment period as the percentage of the cumulative number of tablets taken $[100 * (\text{cumulative number of tablets taken}) / (\text{expected cumulative number of tablets for the subject's treatment duration})]$. For subjects who completed the 29-day treatment period, the expected cumulative number of tablets should be 13. For subjects who were permanently discontinued study treatment or early withdrew from the study, following algorithm will be used to calculate the “expected cumulative number of tablets” taken from each bottle during the treatment period:

1. Determine the expected “dose day”, where “dose day” is defined as days since the first dose date. (i.e. dosing date – first dose date +1)

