 - a. For a subject who receives dialysis 3-5 times per week and starts dosing on Monday or Tuesday, the expected dose days are: 1, 3, 5, 8, 10, 12, 15, 17, 19, 22, 24, 26, and 29.
 - b. For a subject who receives dialysis 3-5 times per week and starts dosing on Wednesday or Thursday, the expected dose days are: 1, 3, 6, 8, 10, 13, 15, 17, 20, 22, 24, 27, and 29.
 - c. For a subject who receives dialysis 3-5 times per week and starts dosing on Friday or Saturday, the expected dose days are: 1, 4, 6, 8, 11, 13, 15, 18, 20, 22, 25, 27, and 29.
2. Determine the “expected cumulative number of tablets” by comparing the last dose day (last dose date – first dose date +1) with the expected dose days. For example, for a subject who received dialysis 3 times per week and started dosing on Wednesday, if the subject’s last dose day is day 7, then the expected cumulative number of tablets taken from a bottle should be 3 (because the last dose was administered before the fourth dose day); if the subject’s last dose day is day 8, then the expected cumulative number of tablets taken from a bottle should be 4 (because the last dose was administered on the fourth dose day).
3. For all other situations which is not covered in step “1” (i.e. a subject who does not receive dialysis 3-5 times per week and/or does not start dosing on Monday – Saturday), the following formula will be used to estimate the “expected cumulative number of tablets” taken from each bottle during the treatment period:

$$\text{Expected cumulative number of tablets} = \text{round}((i - 1) * 3/7, 1) + 1$$

Where “i” is the “last dose day”.

Overall compliance for a subject is categorized as follows: >0% and <80% if compliance for at least one bottle is <80%, 80% to 120% if compliance for all three bottles is between 80% and 120%, and >120% otherwise.

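### SAP 6.2.6 uses 13 expected doses for every completer, although a permitted Day 27 final visit has 12 on the SAP's own calendar

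*SAP*

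**What the plan says.** SAP 6.2.6 builds two descriptive measures on an expected count. The average three-times-weekly dose is the cumulative dose taken divided by expected doses. Compliance, computed bottle by bottle, is tablets taken divided by the "expected cumulative number of tablets for the subject's treatment duration". For completers both denominators are a constant: "For subjects who completed the 29-day treatment period, the expected number of doses during the treatment period is 13", and likewise 13 tablets per bottle. Subjects who stopped treatment or withdrew are handled differently: their last dose day is compared with a calendar chosen by the weekday of the first dose. Two of those calendars matter here:

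- calendar b: "Wednesday or Thursday, the expected dose days are: 1, 3, 6, 8, 10, 13, 15, 17, 20, 22, 24, 27, and 29"
- calendar c: "Friday or Saturday, the expected dose days are: 1, 4, 6, 8, 11, 13, 15, 18, 20, 22, 25, 27, and 29"

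On timing, Protocol 4.2 allows a window of two days either way: it "days is allowed for visits during the Treatment period". It also says "At Day 29, all subjects will receive their last dose of study treatment". For three-times-weekly dialysis, Protocol section 7 adds that "the Day 1, 15 and 29 study visit must not occur on the first dialysis session of the week".

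SAP 11.1.2, number 04, makes compliance below 80% or above 120% for any bottle a potential per-protocol exclusion. It separately lists missed doses: two in a row, or three not in a row. SAP section 4 adds: "The Per-Protocol population will not be analyzed if this population comprises more than 80% of the Intent-To-Treat population".

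**The concern.** The denominator is described as depending on how long the subject was treated, yet for completers it does not vary. The completer population in SAP section 4 is defined by finishing the Day 29 assessments, not by being seen on calendar Day 29, so someone seen two days early or late is still a completer. A fully adherent subject can therefore appear to have missed a dose or taken an extra one.

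Identical dosing can also be scored in two ways. A Friday starter who takes 12 doses, the last on Day 27, scores 12/12 = 100% if recorded as discontinued and 12/13 = 92.3% if recorded as a completer.

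At stake are the exposure and compliance tables and one trigger for per-protocol exclusion.

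**Working it through.** **The plan's own figure.** Calendars a, b and c in SAP 6.2.6 each list 13 dose days through Day 29. The SAP's step 3 formula for other cases agrees: (29 − 1) × 3/7 = 12, and 12 + 1 = 13. So 13 is right when the last scheduled dose falls on Day 29.

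**Which other final days are possible.** Inputs are the ±2-day window (Days 27 to 31), dosing on dialysis days, and the bar on the first session of the week for Day 1 and Day 29 visits. For the two usual three-times-weekly patterns, the expected doses by final visit day are:

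| Pattern and start | Day 27 | Day 29 | Day 31 |
|---|---|---|---|
| Mon-Wed-Fri, Wednesday | Monday, barred | 13 | Friday, 14 if dosing continues |
| Mon-Wed-Fri, Friday | Wednesday, 12 | 13 | Sunday, no dialysis |
| Tue-Thu-Sat, Thursday | Tuesday, barred | 13 | Saturday, 14 if dosing continues |
| Tue-Thu-Sat, Saturday | Thursday, 12 | 13 | Monday, no dialysis |

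Days 28 and 30 are never dialysis days in these patterns.

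The 12 is a direct count of calendar c through Day 27. The 14 is calendar b's 13 plus the next session on Day 31, which the SAP does not list. As a cross-check only, because step 3 is written for other subjects: (27 − 1) × 3/7 = 11.1, rounded to 11, plus 1 = 12; (31 − 1) × 3/7 = 12.9, rounded to 13, plus 1 = 14.

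**Effect under full adherence.** Day 27: 12/13 = 92.3%, so 7.7% low. Day 31: 14/13 = 107.7%, so 7.7% high. The denominator itself is off by 13/12 − 1 = +8.3% or 13/14 − 1 = −7.1%. The reported average dose is the arm dose times the same factor:

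| Arm | × 12/13 | × 14/13 |
|---|---|---|
| 10 mg | 9.2 mg | 10.8 mg |
| 15 mg | 13.8 mg | 16.2 mg |
| 25 mg | 23.1 mg | 26.9 mg |
| 30 mg | 27.7 mg | 32.3 mg |

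**Effect at the 80% limit.**

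- Day 27, two non-consecutive misses: 10/13 = 76.9% under the SAP, 10/12 = 83.3% on the calendar count. The subject is flagged for compliance, although the missed-dose rule is not met.
- Day 31, three misses: 11/13 = 84.6% under the SAP, 11/14 = 78.6% on the extended count. The descriptive category changes, but the missed-dose rule still catches the subject.

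**The case against.** The best defence is that 13 is a deliberate convention: completers are measured against the planned 29-day course. Protocol 4.2 and SAP 11.4.1 both describe treatment as running to Day 29, and SAP 11.5.3 uses planned time for derived quantities unless stated otherwise. On that view, a subject who finishes on Day 27 did receive 12 of 13 planned doses. This defends the number 13 but not its fit with the denominator that 6.2.6 itself defines by the subject's treatment duration; that specific definition outranks the general convention. A strictly literal 29-day reading does not help either: a Day 27 completer would then be neither a completer nor a discontinuation, and no rule would apply.

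Three parts of the defence stand.

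- **The Day 31 count is an inference.** No text schedules a 14th dose, and the window is written for visits. Giving the last dose at the visit makes continued dosing plausible but does not establish it.
- **The one consequential flag is guarded.** SAP 11.1.2 equates falling below 80% with three or more missed doses over 29 days, which is correct for a 13-dose course, so a reviewer could notice that two misses fall short. Flagged cases go to the clinical team, and the per-protocol analysis runs only if that population is 80% or less of ITT.
- **7.7% is a per-subject figure.** Day 29 falls on the same weekday as Day 1, so on three-times-weekly dialysis it is always a permitted session and only a moved visit triggers the problem. Assuming one affected subject among 15 in an arm, the arm mean shifts by about 7.7%/15 = 0.5%. Early and late visits pull in opposite directions.

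**Conclusion.** The inconsistency is real and small. The firm part is the Day 27 case: a Friday or Saturday starter on three-times-weekly dialysis has 12 expected doses on the SAP's own calendar and is divided by 13. The Day 31 case holds only on the assumption that dosing continues at each session until a late visit.

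A reader might infer more, and the documents do not support it:

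- That 13 is a miscount. It is exact for a last dose on Day 29.
- That the SAP schedules 14 doses. Its calendars stop at Day 29.
- That arm-level exposure is off by 7.7%. The documents do not say how many final visits fall on Day 27 or Day 31; the number may be zero.
- That efficacy conclusions are at risk. The primary dose-response model uses the ITT population and the randomized dose, not these compliance figures.

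Full adherence stays within 80–120% in either case. This is an optional improvement to the descriptive exposure and compliance tables, and it removes one potentially spurious per-protocol flag.

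**What to change.** In SAP 6.2.6, for completers on three-times-weekly dialysis, set the expected doses and the expected tablets per bottle to the number of step 1 dose days on or before the actual Day 29 visit (visit date − first dose date + 1), with calendar b extended to Day 31. That extension also states openly that dosing runs up to a late visit. Use the visit date rather than the last dose date, so that doses missed at the end of treatment still count as expected.

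Keep 13 for all other completers, including those dialysed four or five times weekly, for whom the documents do not settle whether a dose at an off-calendar visit replaces or adds to a calendar dose. Keep the existing algorithm for subjects who discontinued or withdrew.

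The cost is a wording edit and a small programming change, using visit and dose dates already collected.

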7. PRIMARY STATISTICAL ANALYSES

7.1. Efficacy Analyses

7.1.1. Overview of Planned Efficacy Analyses

The primary efficacy analyses will be based on the “Intent-To-Treat” population, unless otherwise specified.

Table 4 provides an overview of the planned Hgb efficacy analyses, with full details of data displays being presented in Appendix 14: List of Data Displays.

Table 4 Overview of Planned Hgb Efficacy and Sensitivity Analyses based on Emax Model and Other Analyses of Hgb

Endpoint and Related Analyses	Absolute								Change from Baseline							
	Stats Analysis			Summary		Individual			Stats Analysis			Summary		Individual		
	T	F	L	T	F	F	L	T	F	L	T	F	F	L		
Analyses of Hgb change from baseline at Day 29 based on Emax Model																
Posterior Estimates from the Bayesian 3 Parameter Emax Dose-Response Model for the Primary and Sensitivity Prior Analyses and the Estimates from the Frequentist 3 Parameter Emax Dose-Response Model									Y ⁽¹⁾	Y ⁽¹⁾	Y ⁽¹⁾					
Posterior Probability Distribution for Predicted Hemoglobin Change (g/dL) from Baseline at Day 29 Based on Primary Analysis										Y						
Density Plots Associated with Emax Model Parameter, E0										Y						
Density Plots Associated with Emax Model Parameter, Emax										Y						
Density Plots Associated with Emax Model Parameter, ED50										Y						
Density Plots Associated with Emax Model Parameter,										Y						

Endpoint and Related Analyses	Absolute							Change from Baseline						
	Stats Analysis			Summary		Individual		Stats Analysis			Summary		Individual	
	T	F	L	T	F	F	L	T	F	L	T	F	F	L
Variance														
Posterior Predictive Distribution for Hemoglobin (g/dL) Change from Baseline at Day 29 for a Future Subject based on Primary Analysis									Y					
Posterior Predictive Probability that Day 29 Hemoglobin (g/dL) Change for a Future Subject will be in the Range [-0.5, 0.5] g/dL by Daprodustat Dose									Y					
Other Summary and Analyses of Hgb														
Hgb Imputations				Y										
Dose-Response Linear Model for Change in Hemoglobin at Day 29								Y ^[2]						
Linear Model between the corresponding QD and TIW doses with the same Change in Hemoglobin at Day 29								Y						
Summary of Dose Ratio Between Three-Times Weekly Doses (Observed) and QD Doses	Y													
Summary of Dose Ratio Between Three-Times Weekly Doses and QD Doses at Selected Hgb Responses	Y													
Summary of Posterior Estimates from the Bayesian 3 Parameter Emax Dose-Response Model and the Estimates from the Frequentist 3 Parameter Emax Dose-Response Model for Change in Hemoglobin at Week 4 (Based on PHI113633)								Y						

Endpoint and Related Analyses	Absolute							Change from Baseline						
	Stats Analysis			Summary		Individual		Stats Analysis			Summary		Individual	
	T	F	L	T	F	F	L	T	F	L	T	F	F	L
data excluding Japan)														
Dose-Response Linear Model for Change in Hemoglobin at Week 4 (Based on PHI113633 data excluding Japan)								Y						
Scatter Plot of Hgb Response vs. TIW/QD Weekly Dose												Y		
TIW Doses vs. QD Doses Corresponding Selected Hgb Responses												Y		

NOTES :

- T = Table, F = Figure, L = Listing, Y = Yes display generated.
- Stats Analysis = Represents TFL related to any formal statistical analyses (i.e. modelling) conducted.
- Summary = Represents TFL related to any summaries (i.e. descriptive statistics) of the observed raw data.
- Individual = Represents FL related to any displays of individual subject observed raw data.

[1] Primary analysis based on ITT population will be repeated for completer and per protocol populations.

[2] This linear regression analysis will be repeated for ITT, completer, and per protocol populations.

7.1.2. Planned Hgb Efficacy Statistical Analyses

Primary Statistical Analyses
Endpoint(s)

 • Hgb change from baseline at Day 29
Model Specification

 • The primary endpoint is change in Hgb from baseline at Day 29. To model the dose-response relationship a three-parameter Emax model is planned, where Emax is assumed an appropriate model based on the biology and QD-dose-response modeling completed to date for GSK1278863. 
This model assumes the following form:
 $\Delta Hgb = E0 + \frac{(Emax - E0)}{1 + \left(\frac{ED50}{dose}\right)} + \epsilon$ 
Where:
 
 • ΔHgb is the change in Hgb from baseline at Day 29 • E0 is the placebo response • Emax is the maximum response

Primary Statistical Analyses											

 ED50 is the dose that attains the intermediate response, i.e. where $(E_0 + E_{max}) / 2$, is attained ϵ is a random error assumed to be normally distributed with mean zero and constant variance (σ^2) 
The observed change in Hgb from baseline at Day 29 will be used as the response variable in the Emax model. Subjects who have a Day 15 Hgb measurement but a missing Day 29 Hgb measurement will be included with a Day 29 value imputed (see Section 11.7.2.1). Any subject who prematurely discontinues dosing prior to Day 15 will be non-evaluable for the dose-response analysis.
											
Prior Distribution											

The Emax model will be fitted using Bayesian statistical methods (i.e. a posterior Emax model). Prior distributions for each of the model parameters have been based on the estimates obtained from GSK study PHI113633. This modeling provides confidence in setting prior distributions for E0, however, there is greater uncertainty in the estimation of Emax and ED50, which will be explored in sensitivity analyses with alternative (weaker) prior distributions.
											

Prior Distributions of the Primary Model
 
  
 Emax Model Parameters	Bayesian Priors	
   
 E0	~Normal (-0.67, (0.146)²)	
 
 Emax	~Normal (5.26, (1.337)²)	
 
 ED50	~Uniform (10, 120)	
 
 Tau (1/σ^2)	~Gamma (1,1)	
  
		Emax Model Parameters	Bayesian Priors	E0	~Normal (-0.67, (0.146) ²)	Emax	~Normal (5.26, (1.337) ²)	ED50	~Uniform (10, 120)	Tau (1/ σ^2)	~Gamma (1,1)
Emax Model Parameters	Bayesian Priors										
E0	~Normal (-0.67, (0.146) ²)										
Emax	~Normal (5.26, (1.337) ²)										
ED50	~Uniform (10, 120)										
Tau (1/ σ^2)	~Gamma (1,1)										
Model Fitting in SAS											

The model will be fitted in SAS using the MCMC procedure.
 
 Blocking: Sampling blocks of parameters instead of the parameters separately may speed up the convergence to the target distribution. Blocks are specified in the PARMS statement. Seed: The seed for reproducibility of results will be set to 123. 											
Starting Values											

In order to check the validity of the Emax model fit, five separate Monte Carlo Markov Chain's chains will be fitted each with the following starting points:
 
 Chain 1) E0 = -1.2, Emax = 5.5, ED₅₀ = 50, var = 1 Chain 2) E0 = -0.75, Emax = 7, ED₅₀ = 22.5, var = 2 Chain 3) E0 = -1.65, Emax = 4, ED₅₀ = 80, var = 0.5 											

Primary Statistical Analyses
 
 ▪ Chain 4) $E_0 = -1.65$, $E_{max} = 7$, $ED_{50} = 22.5$, $var = 1$ ▪ Chain 5) $E_0 = -0.75$, $E_{max} = 4$, $ED_{50} = 100$, $var = 2$ 
When the starting values are taken in an area where the posterior probability is low, it may take a long time to escape from the starting positions and mixing could be low initially. In this case, other starting values could be tried.

Burn In
 
“Burn-in” is the portion of the chain where convergence has not yet been achieved. “Discarding burn-in” is the practice of discarding the initial portion of a Markov chain. This will be set to 5000 iterations.


Convergence Diagnostics
 
Convergence of the chains to the posterior distribution for each parameter will be assessed using:
 
 • MCMC error of the model parameters • Autocorrelation plot to assess the autocorrelation of each parameter • Visual inspection of the trace plots for each parameter • Gelman and Rubin Diagnostics 
The following points will be reviewed and evaluated:
 
 1. Monte Carlo Standard Error (MCSE) is the standard error of the posterior mean estimate and provides the measurement of the accuracy of the posterior estimates. All parameters MCSE/SD will be derived. All MCMC chains will be run until the posterior estimates of the variance, E_0, the minimal effective dose (MED) and the target dose (TD) have MCSE/SD values of < 0.015 and E_{max}, ED_{50} and the doses of GSK1278863 that achieve a -0.25, 0.25, 0.5, 0.75 and 1 g/dL change over 29 days have MCSE/SD of < 0.05. Note the MCSE/SD criteria for all parameters must be met. 2. Autocorrelation measures dependency among Markov chain samples. When the autocorrelation takes many sample iterations to reduce, this indicates poor mixing of the Markov chain. When the autocorrelation reduces more quickly over time, this indicates good mixing. Autocorrelation plot will be generated for all chains for visual inspection. 3. A visual inspection of all parameters associated trace plots will be performed to assess the mixing of the 5 chains – to check if each chain is independently realizing values similar to the other chains. This is shown by the chain having a constant mean and variance, and by moving around the parameter space freely (i.e. the plot resembles random noise). 4. Gelman and Rubin diagnostics (Gelman and Rubin, 1992; Brooks and Gelman, 1997) are based on analysing multiple simulated MCMC chains by comparing the variances within each chain and the variance between chains. Large deviation between these two variances indicates non-convergence. A refined version of the

Primary Statistical Analyses

potential scale reduction factor (PSRF) as suggested by Brooks and Gelman, (1997) will be calculated for each parameter using the autocall macro %gelman in SAS. The significance level (alpha) of this test will be set to 0.002. A large PSRF indicates that the between-chain variance is substantially greater than the within-chain variance, so that longer simulation is needed. A PSRF < 1.05 suggests that each of the 5 chains has stabilized, and they are likely to have reached the target posterior distribution.

From the above review, if it is felt the burn-in is inadequate as evidenced by (3) and (4), then this will be increased in increments of 5000 iterations. After which, a sample size of 100,000 will be obtained from the estimated posterior from each of the 5 chains, for a total sample size of 500,000 iterations. If the chain appears to be mixing slowly as evidenced by (2) and (3), then re-allocation of parameters in the PARM statement or increasing the number of iterations in increments of 10,000 iterations will be investigated. By monitoring these diagnostics and making adjustments to the modelling code as stated above, it is anticipated that that the required parameter precision as stated in (1) will be achieved. If this is not the case, increases in the number of sample iterations and/or incorporation of thinning will be used to ensure the required level of precision is achieved.

Pairwise comparison plot (cross plot) of the posterior sample for all parameters will be created and inspected.

The Deviance Information Criteria (DIC) for the model will also be obtained for reference.

Posterior Estimates

Once the dose response model has been fitted satisfactorily, the posterior distribution of the model parameters (E_0 , E_{max} , ED_{50} , and variance) will be summarized through means, standard deviation, median, MCSE/SD and equal-sided 95% credibility intervals. The predicted value of Hgb value change from baseline on day 29 at a series of doses (range of possible doses from 0 to 50 will be sectioned off into a sequence of 0.5 increments; i.e. dose levels of 0, 0.5, 1.0, 1.5, ..., 25.0..., 50.) will also be monitored and the median and 95% credibility values will be obtained at each dose. The Hgb dose response curve will be plotted as a line through these medians and 95% credibility bands, and overlaid on a scatter plot of the observed data. This estimated dose response curve is a composite best fit at each dose and is not in itself an E_{max} curve.

The model will be used to make the following inferences to describe the dose response relationship:

- Estimation of the three-times weekly minimally effective dose (MED), defined as the smallest dose achieving a change of -0.5 g/dL over 29 days after being switched from ESA. To estimate this value a variable in the PROC MCMC code will be tracked with the MCMC algorithm and calculated as follows where $\Delta Hgb = -0.5$

Primary Statistical Analyses

$$MED = ED50 \left(\frac{\Delta Hgb - E0}{E_{max} - \Delta Hgb} \right)$$

- Estimation of three-times weekly dose levels from the MED in +0.25 g/dL mean Hgb increments, including estimation of the target dose (TD), defined as the three-times weekly dose of GSK1278863 that achieves a 0 g/dL change over 29 days after being switched from ESA will be made. These variables will be calculated similar to the MED, as shown above, where ΔHgb equals -0.25, 0, 0.25, 0.5, 0.75 and 1.

As well as the dose-response Emax curve, the following figures will be produced:

- A posterior probability distribution of predicted Hgb (g/dL) change over 29 days for each treatment group. Separate variables to estimate the predicted Hgb (g/dL) change at day 29 for doses 0, 10, 15, 25, and 30 will be derived and tracked within the MCMC algorithm. The mean and SD will be calculated for each variable. The dose, along with the mean and SD of its corresponding predicted Hgb change at day 29 will be output into a text file, then R or SAS will be used to produce the plot.
- A predictive posterior probability distribution of Hgb (g/dL) change over 29 days anticipated for a future subject, for each treatment group. The PREDDIST statement will be used in PROC MCMC to predict Hgb change from baseline in future subjects, for each of the studied doses.
- Density plots for each Emax parameter showing the prior and posterior distribution for the primary and sensitivity priors analyses overlaid (Sensitivity priors are described below in Section Sensitivity and Supportive Statistical Analyses.) The sample data generated from the MCMC method will be used to plot the posterior density. R or SAS will then be used to produce this plot for each Emax parameter.
- A predictive posterior probability plot over the dose range to describe the probability that dose will maintain Hgb within the range of [-0.5, 0.5] g/dL after 29 days for a future subject. This plot will be used to determine the probability of a future subject achieving Hgb in [-0.5, 0.5] range at each dose. By comparing across doses, evidence will be provided for the expected improvement of one dose over another, and may aid selection of titration doses in phase 3.

Additional Dose Response Modeling

A Frequentist 3-parameter Emax model in the model form defined as above will also be fitted to data. The derived data from this Emax model (estimates of E0, Emax, ED50 and Var along with their standard error, and 95% CI) will be tabulated and a dose-response curve (alongside the primary analysis curve and sensitivity prior analysis) will also be produced.

Primary Statistical Analyses											

If problems are encountered fitting a three parameter Emax model, or if the Emax shape is a poor fit for the data, or a linear relationship looks plausible across the three-times weekly dose range, then a linear model will be considered of the form:
 $\Delta Hgb = E0 + \alpha Dose$ 
Other appropriate models, such as quadratic model and log-transformed dose will also be explored if necessary.
											
Dose Response Exploration											

 A scatter plot will be produced by study with total weekly doses as x-axis, and Hgb responses as y-axis including the combined QD (PHI113633 excluding Japan) and three-times weekly (204836) data. The pattern can be examined to explore whether or not the two regimens with the same weekly dose would have the same response. 											
Dose Ratio Estimation											

Dose ratio between TIW and QD doses that produce the same Hgb response will be estimated by different approaches. The dose ratio that will be used to make an informative decision about conversion of QD initial and maintenance dose regimens to three-times weekly doses/regimens will be based on the totality of the data obtained from different approaches.
 
 The TIW dose response estimations will be obtained from the above fitted models. In addition, the QD dose response estimations will also be obtained by fitting the same models as described above (two Emax models and a linear model) using GSK study PHI113633 data excluding Japan. The prior information and the starting values for the QD Bayesian Emax model is shown below: 
Five separate Monte Carlo Markov Chain's chains will be fitted each with the following starting points:
 
 Chain 1) $E0 = -1.2, Emax = 5.5, ED_{50} = 16, var = 1$ Chain 2) $E0 = -0.75, Emax = 7, ED_{50} = 22.5, var = 2$ Chain 3) $E0 = -1.65, Emax = 4, ED_{50} = 9.5, var = 0.5$ Chain 4) $E0 = -1.65, Emax = 7, ED_{50} = 22.5, var = 1$ Chain 5) $E0 = -0.75, Emax = 4, ED_{50} = 9.5, var = 2$ 
Prior Distributions for QD Bayesian Emax Model
 
  
 Emax Model Parameters	Bayesian Priors	
   
 E0	$\sim \text{Normal}(-1.2, (0.45)^2)$	
 
 Emax	$\sim \text{Normal}(5.5, (1.5)^2)$	
 
 ED50	$\sim \text{Uniform}(5, 50)$	
 
 Tau ($1/\sigma^2$)	$\sim \text{Gamma}(1, 1)$	
  
		Emax Model Parameters	Bayesian Priors	E0	$\sim \text{Normal}(-1.2, (0.45)^2)$	Emax	$\sim \text{Normal}(5.5, (1.5)^2)$	ED50	$\sim \text{Uniform}(5, 50)$	Tau ($1/\sigma^2$)	$\sim \text{Gamma}(1, 1)$
Emax Model Parameters	Bayesian Priors										
E0	$\sim \text{Normal}(-1.2, (0.45)^2)$										
Emax	$\sim \text{Normal}(5.5, (1.5)^2)$										
ED50	$\sim \text{Uniform}(5, 50)$										
Tau ($1/\sigma^2$)	$\sim \text{Gamma}(1, 1)$										

Primary Statistical Analyses

- For each TIW dose (10mg, 15mg, 25mg, and 30mg), the observed mean Hgb response (Hgb change from baseline) at day 29 can be calculated. Using the observed mean Hgb response values as a bridge, the corresponding QD doses will be estimated using Emax models or a linear model. TIW dose divided by the corresponding QD dose will be used to estimate the dose ratio between them. The TIW doses, the observed mean Hgb responses, and the corresponding estimated QD doses, dose ratios, and the 95% CIs (bootstrap CIs or Bayesian credibility intervals) will be displayed in a table.
- Another way to estimate the dose ratios is to use a selected series of Hgb responses. For each Hgb response value (such as a change of 0.25 g/dL), the corresponding TIW dose and QD dose can be calculated using either an Emax model, or a linear model. The possible Hgb responses choices are: a change of -0.5, -0.25, 0, 0.25, 0.5, 0.75, 1 g/dL between baseline and day 29. The Hgb responses, and the corresponding TIW doses, QD doses, Dose ratios, and their 95% CIs (bootstrap CIs or Bayesian credibility intervals) will be presented in a table.
- In the above two methods, fairly similar dose ratios across the doses indicate the dose ratios is not dose-dependent. Under this assumption, the ratio between the estimated ED50s from the TIW Emax model (this study) and the QD Emax model (GSK study PHI113633) would be equivalent to the dose ratio, as well as the ratio between the estimated slopes from the QD linear model (GSK study PHI113633) and three-times weekly linear model (this study).
- An additional way to explore the dose ratio is to draw a TIW dose vs. QD dose plot using the pair of TIW doses and QD doses obtained from the above methods. The appropriate models to investigate the dose ratio will be fitted based on the plot. If the relationship between the TIW doses and the QD doses is linear, then a linear model $Dose_{TIW} = a + bDose_{QD}$ can be fitted. If the relationship between the TIW and QD doses is generally linear and the magnitude of a dose not deviate from zero in a clinically meaningful way, then it suggests that the dose ratio is not dose dependent. Otherwise if a shows a clinically meaningful difference from 0 or the relationship between the TIW and QD doses is not linear, then it suggests that the dose ratio may be dose dependent. Additional models may be used to further examine how the dose ratio changes when QD dose changes.
- Although the Emax models and the linear model will be explored to estimate the dose ratio between the TIW and the QD doses, the linear model will be more reliable if it is well-fitted across the TIW and the QD dose range. This is because the QD and TIW dose ranges are expected to only cover the beginning part of the Emax curves. Therefore if any doses lie outside the dose ranges (such as ED50), they will be poorly estimated.
- The 95% bootstrap CI of the estimated dose ratios can be constructed based on the 2.5 percentile and the 97.5 percentile of 1000 bootstrap simulations (Efron and

Primary Statistical Analyses
 
Tibshirani, 1993).
 
 For Bayesian Emax models, the posterior distributions of the estimated doses will be obtained by the PROC MCMC procedure to estimate the dose ratios, of which the 95% Bayesian credibility intervals can be constructed based on the 2.5 percentile and the 97.5 percentile of the 500,000 estimations.

Model Checking & Diagnostics
 
 Refer to Convergence Diagnostics and Posterior Estimates
